6 STATISTICAL CONSIDERATION

6.1 Primary Endpoint

Immediate effects of the rTMS within a laboratory session

6.2 Secondary Endpoint

All effects are evaluated within a laboratory session. Participants will be monitored throughout the study for any adverse events and will be withdrawn from the study if they report any adverse events associated with either the testing or the intervention. Individuals will be withdrawn from the study if they experience any of the following:

- 1) Signs of musculoskeletal injury
- 2) Failure or inability to comply with the study procedures
- 3) Any sign of moderate or severe adverse effects associated with TMS or rTMS.
- 4) Pregnancy

6.3 Statistical Methods

Aim 1. To compare the neural (motor cortex and corticospinal tract) excitability (turning the muscle on) of the anterior thigh muscle (quadriceps) in the symptomatic knee to the asymptomatic knee in participants with knee arthritis. We will examine the associations between neural excitability and clinical measures of pain, pain sensitization, quadriceps strength, walking and balance function, and coping styles.

As a preliminary analysis step, all data will be cleaned and inspected for outliers, missing data and distributional irregularities. Although general linear and mixed linear modeling methods are generally robust to minor violations of distributional assumptions, appreciable departures from normality can compromise statistical tests and estimators. Where error distributions potentially deviate from normality or heteroscedasticity is suspected, or for outcomes expected to be non-normally distributed, departures from normality will be addressed using power transformations where appropriate and/or the use of alternative methods that do not assume normality of outcomes (e.g. nonparametric analyses. We will compare between limb differences and use correlation analyses to examine associations between measures of neural excitability, pain, pain sensitization, quadriceps function, timed-up-and-go test, and catastrophizing. If nonparametric statistical tests are indicated, we will use

two-tailed Wilcoxon Signed Rank tests to examine differences between limbs and two-tailed Spearman Rank-Order correlations to examine associations between variables. The threshold for statistical significance is $p < .05$.

Aim 2. To determine the immediate (within day) effects of rTMS + exercise on the ability to activate the quadriceps muscle and clinical outcomes in people with knee arthritis. The primary outcome variables are quadriceps strength (maximum isometric voluntary contraction) and quadriceps voluntary activation percent (calculated from strength and a brief intense electrical stimulation). Secondary outcome variables are measures of neural excitability from the contralateral motor cortex and hemispheres, pain, pain sensitization, and function (based on the Timed-Up-and-Go test)

We will use a repeated measures analysis of variance (ANOVA), conducted under a mixed modeling framework, to compare outcome variables pre- and post-intervention. Because of its superior statistical properties with small sample sizes, restricted maximum likelihood with Kenward-Roger standard errors will be used in these analyses. The threshold for statistical significance is $p < .05$.

6.4 Sample Size and Power

The sample size for this experiment was explored for the primary variables of interest. These variables are thigh muscle strength from a maximal voluntary isometric contraction (MVIC) and percent voluntary activation. We based the estimates from our preliminary data and available data in the literature (Gibbons, 2010). For muscle strength, the estimated effect size was 0.84 (95% CI: -0.11, 1.7). For central activation ratio, the estimated effect size was 0.84 (95% CI: -0.13, 1.7).

Based on a calculated effect size of 0.84, an α of 0.05 and a power ($1-\beta$) of 0.8, we estimated that 11 subjects are needed. Our measurements may have larger variances than previous studies that used single-pulsed TMS to investigate changes in thigh muscle function. Therefore, we inflated our sample to 20 subjects.

Gibbons CE, [name] BG, Hart JM, Saliba SA, Ingersoll CD. Transcranial magnetic stimulation and volitional quadriceps activation. *J Athl Train*. Nov-Dec 2010;45(6):570-579.

6.5 Interim Analysis

No interim analysis is planned for the statistical analyses. For safety, in the event that two adverse events are classified as either "moderate" or "severe", based on the NC TraCS Safety Monitoring Plan guidelines, the study will be placed on hold in order to reassess the study procedures in order to decrease the risk of another adverse event.

7 STUDY INTERVENTION (drug, device or other intervention details)

Repetitive TMS (rTMS) + Exercise Protocol delivered via pulses in a series using the Magstim Rapid2. The frequency of the repetitive pulses is set to 10 Hz, 5 seconds on and 55 seconds off for 15 minutes to deliver a total of 750 pulses. The intensity will be set at 70% of active motor threshold (AMT). During the on time, the subject will perform an isometric exercise for the thigh muscle at 5% of maximum (MVIC). The subject will rest during the off interval to minimize fatigue. The ratio of "on" to "off" stimulus of rTMS well exceeds the recommended safety guidelines for rTMS maximum safe

duration (Wassermann, 1998). These guidelines recommend that the "off" time be at least twice as long as the duration of the "on" time. We are using a 1:11 ratio. The coil will be encased in a black mesh bag with a plastic mesh between the coil and the scalp to mimic the sham condition. This will allow to allow cooling but hide the intervention condition.

For sham rTMS + Exercise the protocol will be the same with the exception that Mu-metal will be placed between the coil and the scalp. The mu-metal serves as a shield for preventing most of the magnetic energy transmission. The coil will be encased in a black mesh bag to allow cooling but hide the mu material. During the "true" rTMS condition, we will also use the mesh bag over the coil to blind the condition.

8 STUDY INTERVENTION ADMINISTRATION (if applicable)

Participants will be randomized into blocks of 3 in an A:B, B:A order, where A is the "true" intervention session and B is the "sham" control session. Half the subjects will be A:B order and half B:A. The randomization list will be created by the biostatistician.

A research assistant (RA) who is responsible for data collection will be blind to the intervention or control. The RA will leave the room during the rTMS intervention. The second RA will be provided the subject's group assignment by the PI and will then fit the appropriate mesh bag with or without the Mu metal over the TMS coil. The subject will be blind to whether they are receiving rTMS or sham rTMS.

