3.1 Study Design

Aim 1 is a descriptive observational study comparing the symptomatic to the asymptomatic knee and obtaining data to characterize the participant's clinical condition. This will be collected in the first data collection session (Session 1).

Aim 2 is a double blinded, crossover, repeated measures design. Each participant will partake in 2 sessions. (Sessions 2 and 3). One session is the control (sham rTMS + exercise) and one is the intervention (rTMS + exercise). Participants will be randomized into blocks of 3 in an A:B, B:A order, where A is the “true” intervention session and B is the “sham” control session. Half the subjects will be A:B order and half B:A. The randomization list will be created by the biostatistician.

Screening: Individuals who express an interest in participating in the study during the recruitment process, either in person, email, or by phone, will be contacted by a researcher.

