4.2 Intervention/Treatment procedures (by visits)

Laboratory Sessions 2 and 3

Sessions 2 and 3 will be scheduled 1 week apart to allow for wash out of any effects from repetitive TMS (rTMS). The only difference between Session 2 and Session 3 is whether the subject receives rTMS + Exercise or sham rTMS + Exercise. After completing the session 2 pre-testing protocol, the subject will be randomly assigned to receive either the true rTMS or sham rTMS + Exercise intervention. The randomization schedule for the 20 subjects will be generated prior to the onset of the study with assignments only known by the biostatistician. Treatment allocation will be revealed to an investigator performing the rTMS + Exercise intervention after collection of the session baseline measurements. If the subject is allocated to the sham rTMS intervention for Session 2, the subject will receive the "true" rTMS intervention in Session 3 and vice versa.

Measurements from the symptomatic leg only will be made pre and post intervention (true or sham) using the previously evaluations and measurements described in Section 5. Specifically, the pre and post measurements include:

- Pain numeric rating scale (NPRS) for current pain.
- Timed-up-and-go (TUG) - repeated 3 times each time measured
- Pressure pain threshold (PPT) at the 4 leg sites and arm site - repeated 3 times at each site location each time measured
- Thigh muscle function: quadriceps isometric strength (MVIC) and central activation ratio (CAR),
- Single-pulse and double-pulse TMS for cortical and subcortical excitability -
- active motor threshold motor evoked potential (AMT-MEP), cortical inhibition (SICI), and cortical facilitation (ICF)

Repetitive TMS (rTMS) + Exercise Protocol

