9 SAFETY MANAGEMENT

The principal investigator, [name], will oversee data collection monitoring and all issues related to participant safety, data collection protocols, and participant confidentiality. [name] will personally collect any adverse event that occurs during the data collection sessions in the Sports Medicine Research Laboratory.

The participant's vital signs will be taken before any active testing, TMS, or rTMS. If the blood pressure or heart rate is low (< 90 systolic, < 60 diastolic, < 50 beats/min), the participant will be advised of the higher risk of syncope and excluded. If the participant reports being light headed or sleep deprived, the data collection session will be stopped and rescheduled.

All researchers involved with TMS and rTMS will be trained on management of syncope and seizures. We will minimize risk of seizure by screening participants for a seizure history and tailoring each person's TMS intensity to their motor (and indirectly seizure) threshold. We will exclude subjects if they are taking medications that are linked to reducing seizure thresholds. We will minimize hearing damage from rTMS by having all participants wear earplugs to protect their hearing during the TMS sessions.

Before maximum voluntary isometric contraction (MVIC) testing participants will be given a warm-up. Participants will also go through a graded warm up to acclimate to the stimulation needed for quadriceps voluntary activation testing. The 5-minute warm-up prior to testing is designed to reduce the risk of muscle soreness and/or injury during testing. The electrical stimulator will always be connected to the stimulus isolation unit to ensure that the subject is isolated from fluctuations in the building's power supply. Additionally, most members of the research team are certified/licensed health

care providers (Licensed Physical Therapist or Certified Athletic Trainer), and all are trained and certified to provide First Aid and CPR. Any safety concerns (i.e. musculoskeletal injury) would likely be recognized immediately during testing and the research team will monitor participants for adverse events during both testing and intervention sessions.

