10 DATA COLLECTION AND MANAGEMENT

The principal investigator will oversee data collection monitoring and all issues related to participant safety, data collection protocols, and participant confidentiality. All adverse events will be reviewed and investigated by [name], a licensed physical therapist. Data will be reviewed by two investigators to ensure quality at all stages of reduction, post processing and imputation into statistical software packages. All data will be de-identified and stored in secure password protected computers. The principal investigator will randomly check data reduction, post-processing, and imputation at time points throughout the study. We will utilize the REDCap software to secure data management.

Each subject and his/her associated information will be identified by a subject identification number. Code lists linking the subject identification number and his/her name and email address will be viewed by the research team only, and will be secured in the Neuromuscular Research Laboratory on a password-protected computer. Email addresses will be obtained solely for the purpose of contacting participants to schedule testing. All data will be de-identified and stored in electronic format on both the data collection computer and the principal investigator's personal computer, as well as a number of backup storage devices. Computer access will be protected via confidential passwords, and backup devices will be stored in the Neuromuscular Research Laboratory, which is secured via keycard entry.

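### Blocks of 3 for two sequences do not guarantee the stated half-and-half split of 20 subjects, no period term is stated to absorb an imbalance, and the PI who passes on assignments also spot-checks the data with no masking stated

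*Combined protocol and SAP*

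**What the plan says.** **Randomization.** Sections 3.1 and 8 carry the same text: "Participants will be randomized into blocks of 3 in an A:B, B:A order". The letter A denotes the session with active rTMS and B the session with sham. On the resulting split, both sections then say: "Half the subjects will be A:B order and half B:A". The total is 20 subjects (Sections 3.3 and 4.2), and the biostatistician makes the list in advance. No ratio within a block is given, and no constraint on the overall total.

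**Analysis.** Section 6.3 and the SAP give the same sentence for Aim 2: "We will use a repeated measures analysis of variance (ANOVA), conducted under a mixed modeling framework, to compare outcome variables pre- and post-intervention". They add REML with Kenward-Roger standard errors, but name no fixed effects. Period and sequence are not mentioned.

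**Who holds the assignments.** Section 4.2 restricts knowledge of them to the biostatistician, then says: "Treatment allocation will be revealed to an investigator performing the rTMS + Exercise intervention after collection of the session baseline measurements". Section 8 describes another route, in which the second research assistant is given the subject's "group assignment by the PI and will then fit the appropriate mesh bag". Under Section 9 the PI "will oversee data collection monitoring and all issues related to participant safety". Section 10 adds: "The principal investigator will randomly check data reduction, post-processing, and imputation at time points throughout the study". Sections 3.2 and 8 describe only the subject and the data-collecting research assistant as blind.

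**The concern.** The block size and the target split do not agree, so the biostatistician cannot build the list from the protocol without adding an unwritten rule.

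In a two-period crossover, unequal sequences matter when the pre-to-post change itself differs between the first and second intervention session, for instance through practice or familiarity with the maximal-contraction test. Unless the model contains period, part of that difference enters the rTMS-minus-sham estimate. Even with equal sequences, an unmodelled period difference inflates the residual variance and costs power.

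The second issue is separate. Section 8 implies that the PI holds the assignments, and Section 10 has the PI checking processed data while the study runs. In a trial called double-blind, checks by someone who knows the condition are an avoidable weak point.

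**Working it through.** **Inputs from the documents.** Block size 3, two sequences, half and half (Sections 3.1 and 8); N = 20 (Sections 3.3 and 4.2); effect size 0.84 (Section 6.4).

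**Assumptions.** The 0.84 is read as a paired effect, in SDs of the within-subject rTMS-minus-sham difference. The documents give no period difference in pre-to-post change, so 0.25, 0.5 and 0.75 of the same SD are used. Tests are two-sided at 5%.

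**1. Can the rule deliver 10:10?** 3/2 = 1.5 subjects per sequence per block, so no block is balanced, and 20 = 6 × 3 + 2. Let each block be 2:1 or 1:2 with probability 1/2. The A:B count in six full blocks is 6 + Bin(6, 1/2). The last two places add 0, 1 or 2 with probabilities 1/6, 2/3 and 1/6. Then

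P(10:10) = (15/64)(1/6) + (20/64)(2/3) + (15/64)(1/6) = 110/384 = 55/192 = 28.6%.

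The remaining splits, counted in either direction, are 11:9 43/96 = 44.8%; 12:8 5/24 = 20.8%; 13:7 5/96 = 5.2%; 14:6 1/192 = 0.5%. So 13:7 or worse occurs in 5.7% of lists.

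The result depends on how the rule is read. If 2:1 and 1:2 blocks alternate, 10:10 occurs in 66.7% of lists and 11:9 in the rest. If every block is 2:1, the split is always 13:7 or 14:6. No reading guarantees 10:10.

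**2. Bias without a period term.** Let P be the period difference in pre-to-post change. The rTMS-minus-sham difference has mean τ + P in sequence A:B and τ − P in B:A, so the overall mean is τ + P(nAB − nBA)/20. With P = 0.5 SD the bias is (4/20)(0.5) = 0.10 SD at 12:8, 0.15 SD at 13:7 and 0.20 SD at 14:6. A shift in level between visits cancels in the change and adds nothing.

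**3. Type I error without a period term** (simulated paired t-test, n = 20, 200,000 trials per cell):

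| Split | P = 0.25 SD | P = 0.5 SD | P = 0.75 SD |
|---|---|---|---|
| 10:10 | 4.4% | 2.9% | 1.5% |
| 11:9 | 4.5% | 3.3% | 2.1% |
| 12:8 | 4.9% | 4.5% | 3.8% |
| 13:7 | 5.5% | 6.5% | 7.4% |
| 14:6 | 6.4% | 9.6% | 13.4% |
| Average over lists | 4.6% | 3.6% | 2.6% |

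With a period term (t-test on 18 df) the error is 4.9% to 5.1% in every cell.

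**4. Power at effect 0.84, n = 20.** With no period effect and no period term, the noncentral t on 19 df, with noncentrality 0.84 × √20 = 3.76, gives 94.5%. With P = 0.5 SD and no term, the expected sample variance at 10:10 rises from 1 to 1 + 0.25 × 20/19 = 1.26, and simulated power is 91%. At 12:8 it is 82% or 96%, depending on the direction of the period difference. With the term, simulated power is 94.5% at 10:10 (noncentral t on 18 df: 94.4%) and 93.5% at 12:8.

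**5. Masking, read side by side.** Section 4.2: assignments are known to the biostatistician and later revealed to whoever delivers the rTMS. Section 8: the PI tells the second research assistant, so the PI must hold them, and no timing is given. Section 10: the PI checks data processing during the study. Section 10 calls the data de-identified, but that removes identity, not condition. No arithmetic applies here.

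**The case against.** **The block size alone costs little.** Averaged over possible lists, type I error without a period term is below 5%. At P = 0.5 SD, average power is 90.3% against 91.1% at a forced 10:10. This stands: the period term matters more than the block size.

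**The harm rests on an assumed period difference.** The protocol expects effects to wash out within hours and leaves a week between sessions. At P = 0.25 SD, the power lost at 10:10 is under one percentage point. This also stands. But washout limits carryover, not practice effects, and a two-period crossover analysis should not have to assume there are none.

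**The biostatistician could simply choose a balanced list.** True, since half and half is stated and the list is made in advance. That would be an unwritten correction to the written rule.

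**The masking point rests on silence.** Nothing says the PI's checks are unmasked. The primary outcomes are dynamometer torque and a ratio from it, collected by a blinded assistant who leaves the room during treatment, and Section 10 also has two investigators review the data. All of this limits the risk. What remains is that Sections 4.2 and 8 disagree on who holds the assignments, and that no masking is stated for the person who both passes them on and checks the data.

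**The simulation is a stand-in** for the planned REML model. It has to be, because that model's terms are not stated.

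**Conclusion.** The concern holds and should be fixed. The written rule does not deliver the allocation the plan states: 10:10 arises in 28.6% of lists if blocks are randomly 2:1 or 1:2, and between 0% and 66.7% under the other readings tried.

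The statistical consequence is usually modest. Without a period term, type I error exceeds 5% only at 13:7 or worse (5.7% of lists under the random reading). A 0.5 SD period difference costs about 3.5 percentage points of power even at 10:10. These error and power figures rest on the assumed range of 0.25 to 0.75 SD, and the power figures also on reading 0.84 as a paired effect.

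On masking, the finding is a gap and an internal conflict in the text. It is not evidence that bias has occurred, and it has no numerical size.

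**What to change.** 1. **Sections 3.1 and 8:** replace blocks of 3 with permuted blocks of 4, each with two A:B and two B:A. Five blocks give exactly 10:10 as randomized. Another even size that divides 20 also works; blocks of 6 leave two subjects over. Withdrawals can still unbalance the analysed set, which the next item covers.
2. **Section 6.3 and the SAP:** list the mixed model's fixed effects and include period.
3. **Sections 4.2 and 8:** have the biostatistician supply concealed, sequentially numbered assignments directly to the second research assistant, opened after the session pre-test. Delete the PI from this route, and make 4.2 and 8 agree on who receives the assignment and who delivers the stimulation. If the PI delivers it, removing the PI from the hand-over does not mask the PI, and item 4 has to carry the protection.
4. **Section 10:** state that the PI's checks are made on data masked to condition until data reduction is complete, and that the PI can obtain an assignment when the safety oversight in Section 9 requires it.

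**Cost.** A new 20-line list and wording edits in Sections 3.1, 4.2, 6.3, 8, 10 and the SAP. The period term uses one degree of freedom: with no period effect, power at 10:10 moves from 94.5% to 94.4%. No added subjects, visits or staff are needed; the biostatistician and the second research assistant are already in the plan.

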9 SAFETY MANAGEMENT

The principal investigator, [name], will oversee data collection monitoring and all issues related to participant safety, data collection protocols, and participant confidentiality. [name] will personally collect any adverse event that occurs during the data collection sessions in the Sports Medicine Research Laboratory.

The participant's vital signs will be taken before any active testing, TMS, or rTMS. If the blood pressure or heart rate is low (< 90 systolic, < 60 diastolic, < 50 beats/min), the participant will be advised of the higher risk of syncope and excluded. If the participant reports being light headed or sleep deprived, the data collection session will be stopped and rescheduled.

All researchers involved with TMS and rTMS will be trained on management of syncope and seizures. We will minimize risk of seizure by screening participants for a seizure history and tailoring each person's TMS intensity to their motor (and indirectly seizure) threshold. We will exclude subjects if they are taking medications that are linked to reducing seizure thresholds. We will minimize hearing damage from rTMS by having all participants wear earplugs to protect their hearing during the TMS sessions.

Before maximum voluntary isometric contraction (MVIC) testing participants will be given a warm-up. Participants will also go through a graded warm up to acclimate to the stimulation needed for quadriceps voluntary activation testing. The 5-minute warm-up prior to testing is designed to reduce the risk of muscle soreness and/or injury during testing. The electrical stimulator will always be connected to the stimulus isolation unit to ensure that the subject is isolated from fluctuations in the building's power supply. Additionally, most members of the research team are certified/licensed health

care providers (Licensed Physical Therapist or Certified Athletic Trainer), and all are trained and certified to provide First Aid and CPR. Any safety concerns (i.e. musculoskeletal injury) would likely be recognized immediately during testing and the research team will monitor participants for adverse events during both testing and intervention sessions.

The research team will refer any individuals who experience adverse events to the Stallings-Evans Sports Medicine Center (located in the building adjacent to Fetzer Hall where the Neuromuscular and Sports Medicine Research Laboratories are located) or Emergency Medical Services depending on the nature and severity of the adverse event issues.

Adverse events will be determined using the NC TraCS Safety Monitoring Plan guidelines for Minimal Risk Studies. The Grading Scale is as follows:

Mild - Event results in mild or transient discomfort, not requiring intervention or treatment; does not interfere with daily activities (e.g. transient muscle soreness)

Moderate - Event is sufficiently discomforting so as to limit or interfere with daily activities; may require additional interventional treatment (e.g. musculoskeletal injury such as a muscle strain)

Severe - Event results in significant symptoms that prevent normal daily activities; may require invasive intervention

In the event that two adverse events are classified as either moderate or severe the study will be placed on hold in order to reassess the study procedures in order to decrease the risk of another adverse event.

